5.4.2. Subgroups regarding patient characteristics

Subgroup analyses of safety will be performed with respect to the patient characteristics defined in Section 8.2.2.

Subgroup analyses of safety will also be performed with respect to the following factors:

- Complication of hepatic function disorder [absent or present]
- Complication of renal impairment [absent or present]
- Pediatric (<15 years), adult (≥15 to <65 years), or elderly (≥65 years)
- Past history of hepatitis B virus carrier [absent or present]
- Complication of hepatitis B virus carrier [absent or present]
- Pregnancy (present)
- Prior treatment with a 5-aminosalicylic acid preparation [absent or present]
- Prior treatment with steroid [absent or present]
- Prior treatment with an immunomodulator (azathioprine or 6-mercaptopurine) [absent or present]
- Prior treatment with tacrolimus [absent or present]
- Prior treatment with a biologic agent [absent or present]

In addition, subgroup analyses of safety will be performed for contraindicated patients (patients to whom administration of this drug may be contraindicated according to the package insert of this drug) using separately-specified criteria to extract eligible patients.

Subgroup analyses of effectiveness will be performed with respect to the following patient characteristics:

- Complication of hepatic function disorder [absent or present]
- Complication of renal impairment [absent or present]
- Pediatric (<15 years), adult (≥15 to <65 years), or elderly (≥65 years)
- Prior treatment with steroid [absent or present]
- Absence or presence of refractory UC based on treatment responsiveness [absent, steroid-resistant, steroid-dependent, present but not steroid-dependent or steroid-resistant]
- Prior treatment with an immunomodulator (azathioprine or 6-mercaptopurine) [absent or present]
- Prior treatment with tacrolimus [absent or present]
- Prior treatment with a biologic agent [absent or present]
- Effectiveness of prior biologics (no prior use, 1st line ineffective, 2nd line ineffective, indeterminate)

6. ENDPOINTS AND COVARIATES

6.1. Safety Endpoints

The safety endpoints and their definition in this study are presented below. Events assessed as a safety endpoint will be those that developed from the start of treatment to the end of observation period or 60

weeks after the start of treatment, whichever came first, except for malignancies, for which all events occurring by the end of observation period will be assessed as a safety endpoint.

- Adverse reactions: Adverse events considered by the physician as treatment-related
- Adverse events (AEs): All-causality AEs
- Serious adverse events (SAEs) and serious adverse reactions: AEs and adverse reactions considered by the physician as serious
- Safety specification: The definition of the events considered as an element in the safety specification of this drug should follow the definition of the Important Identified Risks and Important Potential Risks presented in the Appendix of the latest Tofacitinib Periodic Safety Update Report (PSUR). Below is the definition at the time of the preparation of this SAP (3.0 version), except for hepatitis B virus reactivation, of which definition is given in this SAP below, because it is not defined in the PSUR.
 - Serious infections (including tuberculosis, pneumonia, pneumocystis pneumonia, sepsis, opportunistic infection): Events that are serious and coded as MedDRA SOC Infections and Infestations; MedDRA HLT Tuberculous infections, Mycobacteria identification and serology; MedDRA PT Febrile neutropenia, Asymptomatic COVID-19, Coronavirus infection, Coronavirus test positive, Coronavirus test, COVID-19 immunisation, COVID-19 pneumonia, COVID-19 prophylaxis, COVID-19 treatment, COVID-19, Exposure to SARS-CoV-2, Occupational exposure to SARS-CoV-2, SARS-CoV-2 antibody test, SARS-CoV-2 antibody test positive, SARS-CoV-2 carrier, SARS-CoV-2 sepsis, SARS-CoV-2 test false negative, SARS-CoV-2 test positive, SARS-CoV-2 test, SARS-CoV-2 viraemia, or Suspected COVID-19
 - Herpes zoster: Events coded as MedDRA PT Disseminated varicella zoster virus infection,
 Genital herpes zoster, Herpes zoster cutaneous disseminated, Herpes zoster
 disseminated, Herpes zoster infection neurological, Herpes zoster meningitis, Herpes zoster
 meningoencephalitis, Herpes zoster meningomyelitis, Herpes zoster necrotising retinopathy,
 Herpes zoster oticus, Herpes zoster pharyngitis, or Ophthalmic herpes zoster
 - Neutrophils decreased, lymphocytes decreased, and haemoglobin decreased: Events retrieved by MedDRA SMQ Haematopoietic erythropenia (Broad and Narrow); or coded as MedDRA PT Agranulocytosis, Band neutrophil count decreased, Band neutrophil percentage decreased, Cyclic neutropenia, Febrile neutropenia, Granulocyte count decreased, Granulocytopenia, Idiopathic neutropenia, Neutropenia, Neutropenic infection, Neutropenic sepsis, Neutrophil count decreased, Neutrophil percentage decreased, B-lymphocyte count decreased, Lymphocyte count decreased, Lymphopenia, T-lymphocyte count decreased, or Lymphocyte percentage decreased
 - Hepatic function disorder: Events retrieved by MedDRA SMQ Drug related hepatic disorders severe events only (Narrow); or coded as MedDRA PT Alanine aminotransferase increased,
 Aspartate aminotransferase increased, Hepatic enzyme increased, or Transaminases increased
 - Hepatitis B virus reactivation: Events associated with hepatitis B that developed in patients with
 past history of hepatitis B virus carrier or with a complication of hepatitis B virus carrier

- Gastrointestinal perforation: Events retrieved by MedDRA SMQ Gastrointestinal perforation
 (Narrow); or coded as MedDRA PT Abscess bacterial, Abscess rupture, Appendicectomy,
 Appendicitis, Biliary abscess, Colitis, Diverticulitis, Diverticulum, Gallbladder abscess, Liver
 abscess, Pancreatic abscess, Pelvic abscess, Perihepatic abscess, Postoperative abscess, Pyloric
 abscess, Rectovaginal septum abscess, Splenic abscess, or Subdiaphragmatic abscess
- Interstitial lung disease: Events retrieved by MedDRA SMQ Interstitial lung disease (Broad and Narrow)
- Venous thromboembolism: Events retrieved by MedDRA SMQ Embolic and thrombotic events, venous (Narrow)
- Malignancy: Events retrieved by MedDRA SMQ Malignancy related conditions (Narrow),
 Malignancy related therapeutic and diagnostic procedures (Narrow), Malignant or unspecified tumours (Narrow), or Tumour markers (Narrow)
- Cardiovascular events (including lipids increased and hyperlipidaemia): Events retrieved by MedDRA SMQ Myocardial infarction (Narrow), Other ischaemic heart disease (Narrow), or Central nervous system vascular disorders (Narrow); or coded as MedDRA PT Cardiac failure congestive, Sudden cardiac death, Cardiac death, Pulmonary embolism, Acquired mixed hyperlipidaemia, Apolipoprotein B/Apolipoprotein A-1 ratio increased, Autoimmune hyperlipidaemia, Blood cholesterol abnormal, Blood cholesterol esterase increased, Blood cholesterol increased, Blood triglycerides abnormal, Blood triglycerides increased, Diabetic dyslipidaemia, Dyslipidaemia, Familial hypertriglyceridaemia, High density lipoprotein abnormal, High density lipoprotein decreased, Hypercholesterolaemia, Hyperlipidaemia, Hypertriglyceridaemia, Hypo HDL cholesterolaemia, Intermediate density lipoprotein increased, LDL/HDL ratio increased, Lipid metabolism disorder, Lipids abnormal, Lipids increased, Lipoprotein (a) abnormal, Lipoprotein (a) increased, Low density lipoprotein abnormal, Low density lipoprotein increased, Non-high-density lipoprotein cholesterol increased, Remnant hyperlipidaemia, Remnant-like lipoprotein particles increased, Total cholesterol/HDL ratio abnormal, Total cholesterol/HDL ratio increased, Type I hyperlipidaemia, Type II hyperlipidaemia, Type IIa hyperlipidaemia, Type IIb hyperlipidaemia, Type III hyperlipidaemia, Type IV hyperlipidaemia, Type V hyperlipidaemia, Very low density lipoprotein abnormal, or Very low density lipoprotein increased
- Cardiovascular events (excluding lipids increased and hyperlipidaemia): Events retrieved by MedDRA SMQ Myocardial infarction (Narrow), Other ischaemic heart disease (Narrow), or Central nervous system vascular disorders (Narrow); or coded as MedDRA PT Cardiac failure congestive, Sudden cardiac death, Cardiac death, or Pulmonary embolism
- Lipids increased and hyperlipidaemia: Events coded as MedDRA PT Acquired mixed hyperlipidaemia, Apolipoprotein B/Apolipoprotein A-1 ratio increased, Autoimmune hyperlipidaemia, Blood cholesterol abnormal, Blood cholesterol esterase increased, Blood cholesterol increased, Blood triglycerides abnormal, Blood triglycerides increased, Diabetic dyslipidaemia, Dyslipidaemia, Familial hypertriglyceridaemia, High density lipoprotein abnormal, High density lipoprotein decreased, Hypercholesterolaemia, Hyperlipidaemia, Hypertriglyceridaemia, Hypo HDL cholesterolaemia, Intermediate density lipoprotein increased, LDL/HDL ratio increased, Lipid metabolism disorder, Lipids abnormal, Lipids increased, Lipoprotein (a) abnormal, Lipoprotein (a) increased, Low density lipoprotein abnormal, Low

NIS Protocol A3921248 Statistical Analysis Plan

density lipoprotein increased, Non-high-density lipoprotein cholesterol increased, Remnant hyperlipidaemia, Remnant-like lipoprotein particles increased, Total cholesterol/HDL ratio abnormal, Total cholesterol/HDL ratio increased, Type I hyperlipidaemia, Type II hyperlipidaemia, Type IIa hyperlipidaemia, Type IIb hyperlipidaemia, Type IV hyperlipidaemia, Type IV hyperlipidaemia, Type V hyperlipidaemia, Very low density lipoprotein abnormal, or Very low density lipoprotein increased

- Rhabdomyolysis and myopathy: Events retrieved by MedDRA SMQ Rhabdomyolysis/Myopathy (Narrow); or coded as MedDRA PT Blood creatine phosphokinase increased
- Time to onset of each element in the safety specification

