6.1.1. Important identified risks

- Serious infection (including tuberculosis, pneumonia, Pneumocystis pneumonia, sepsis, and opportunistic infection)
- Herpes zoster
- Neutropenia, lymphopenia, oligochromemia
- Hepatic impairment
- Reactivation of hepatitis B virus
- Gastrointestinal perforation
- Interstitial lung disease
- Venous thrombosis

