7.3.7.1. Clinical laboratory tests

Results of the following clinical laboratory tests conducted from baseline (within 1 month before treatment commencement, including the date of treatment commencement*) to the date of completion of the observation period (or date of XELJANZ discontinuation).

1. Hematology White blood cell count, neutrophil, eosinophil, lymphocyte, monocyte, red blood cell count, platelet count, hemoglobin

- 2. Blood chemistry AST (GOT), ALT (GPT), AL-P, LDH, total cholesterol, HDL-C, LDL-C, y-GTP, total bilirubin, triglyceride, serum creatinine, creatine kinase, albumin
- 3. Other tests KL-6, -D-glucan, BUN, fecal calprotectin, CRP

*: Within 3 months before treatment commencement for fecal calprotectin

7.3.7.2.Chest X-ray test or chest CT test

Findings of chest X-ray or chest CT conducted from baseline (within 3 months before treatment commencement, including the date of treatment commencement) to the date of completion of the observation period (or date of XELJANZ discontinuation).

7.3.7.3.Tuberculosis screening tests

Results of the following tests conducted from baseline (within 6 months before treatment commencement, including the date of treatment commencement) to the date of completion of the observation period (or date of XELJANZ discontinuation).

- 1. Interferon *y* release assay (QuantiFERON, T-SPOT)
- 2. Tuberculin skin test
- 7.3.7.4.Blood pressure (systolic/diastolic)

Results of measurements from baseline to the date of completion of the observation period (or date of XELJANZ discontinuation).

7.3.7.5.Hepatitis B and C virus tests

Results of the following tests conducted within 3 months before treatment commencement should be recorded. For patients who are HBV carriers, the status of HBV-DNA test conducted up to the completion of the observation period (or date of XELJANZ discontinuation) should be recorded.

- 1. Hepatitis B virus test: HBs antigen, HBs antibody, HBc antibody, and HBV-DNA test
- 2. Hepatitis C virus test: HCV antibody

7.3.7.6.Colonoscopy

Results of colonoscopy (inflammation site and findings) conducted from 6 months before commencement of XELJANZ treatment to the date of completion of the observation period (or date of XELJANZ discontinuation).

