8.2.2. Patient characteristics and medical history

• Patient characteristics

Using the SAS (including subgroups by mean daily dose), set of patients treated for a long term (including subgroups by mean daily dose), and EAS, patients will be, according to the methods described in Section 8.1, summarized with respect to the following patient characteristics:

- Gender [male, female]
- Age (continuous)
- Age [<15 years, ≥15 to <65 years, ≥65 years]
- Age [<50 years, \ge 50 to <65 years, \ge 65 years]
- Body weight (continuous)
- Body weight [$<50 \text{ kg}, \ge 50 \text{ to } <60 \text{ kg}, \ge 60 \text{ to } <70 \text{ kg}, \ge 70 \text{ kg}$]
- BMI (continuous)
- BMI [<18.5, ≥ 18.5 to <25, ≥ 25]
- Diagnosis [ulcerative colitis, other]
- Duration of UC (continuous)
- Duration of UC [<2 years, ≥ 2 to <5 years, ≥ 5 to <10 years, ≥ 10 to <20 years, ≥ 20 years]
- Range of UC [pancolitis, left-sided disease, proctitis, right-sided or segmental disease, other]
- Severity of UC [mild, moderate, severe]
- Refractory UC based on treatment responsiveness [absent, present]
- Refractory UC based on treatment responsiveness [absent, steroid-resistant, steroid-dependent, present but not steroid-resistant or steroid-dependent]
- Past history [absent, present]
- Infections [absent, present]
- Past history of malignancy [absent, present]
- Past history of an autoimmune disease [absent, present]
- Past history of a cardiovascular disease [absent, present]
- Past history of lung disorder [absent, present]
- Past history of gastrointestinal disorder [absent, present]
- Past history of hepatic function disorder [absent, present]
- Hepatic function disorder: past history of hepatitis B [absent, present]
- Hepatic function disorder: past history of hepatitis C [absent, present]
- Hepatic function disorder: past history of hepatitis B virus carrier [absent, present]

- Hepatic function disorder: past history of hepatitis C virus carrier [absent, present]
- Past history of renal impairment [absent, present]
- Past history of metabolic abnormality [absent, present]
- Metabolic abnormality: past history of diabetes mellitus [absent, present]
- Past history of anaemia [absent, present]
- Complications [absent, present]
- Complication of an infection [absent, present]
- Complication of malignancy [absent, present]
- Complication of an autoimmune disease [absent, present]
- Complication of a cardiovascular disease [absent, present]
- Complication of lung disorder [absent, present]

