8.2.3.1. Adverse reactions

• All adverse reactions

Adverse reactions will be summarized by SOC and PT in terms of number and proportion of patients.

Serious adverse reactions

Serious adverse reactions will be summarized by SOC and PT in terms of number and proportion of patients.

• Details of adverse reactions

Adverse reactions in different categories defined with respect to the following factors will be summarized by SOC and PT in terms of number and proportion of patients. For the factor time to onset, the number of patients who took at least one dose during each time category will be used as the denominator to calculate the proportion.

- Seriousness [serious, non-serious]
- Known/unknown [known, unknown]
- Time to onset [≤15 weeks, >15 to ≤30 weeks, >30 to ≤45 weeks, >45 to ≤60 weeks, >60 to ≤75 weeks, >75 to ≤90 weeks, >90 to ≤105 weeks, >105 to ≤120 weeks, >120 to ≤135 weeks, >135 weeks]
- Action taken [permanent discontinuation of treatment, temporary discontinuation or dose reduction, dose increase, no change]
- Outcome [not recovered, resolved/recovered, recovered with sequelae, improved, death, unknown]

Patients who experienced multiple adverse reactions of the same adverse reaction (identical PT) will be summarized as follows:

- For seriousness: Patients who experienced both serious and non-serious adverse reactions of the same PT will be handled as having experienced a serious event.
- For known/unknown: Priority will be given to "unknown" if both experienced.
- For time to onset: The day to the first onset will be used.
- For action taken: If multiple actions were taken, only one kind of action will be adopted with the order of priority being permanent discontinuation, temporary discontinuation/dose reduction, and other (no change or dose increase).
- For outcome: The outcome for the last event will be used.

Safety specification

The following adverse reactions included in the scope of the safety specification will be summarized in terms of number and proportion of patients, as well as incidence and its 95% CI.

- Serious infections (including tuberculosis, pneumonia, pneumocystis pneumonia, sepsis, and opportunistic infection)
- Herpes zoster
- Neutrophils decreased, lymphocytes decreased, haemoglobin decreased
- Hepatic function disorder
- Hepatitis B virus reactivation (in patients with past history or complication of hepatitis B virus carrier)
- Gastrointestinal perforation
- Interstitial lung diseases
- Venous thromboembolism

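### The SAP counts hepatitis B virus reactivation only in patients recorded as carriers, so a reported case in any other patient is left out of that element

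*SAP*

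**What the plan says.** Protocol 6.1.1 and SAP 2.1 both list "Reactivation of hepatitis B virus" among the important identified risks, without restriction.

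For most elements SAP 6.1 follows the periodic safety update report, "except for hepatitis B virus reactivation, of which definition is given in this SAP below, because it is not defined in the PSUR". The SAP's own definition has two parts. The event part is "Hepatitis B virus reactivation: Events associated with hepatitis B that developed in patients with"; the population part that completes it is "past history of hepatitis B virus carrier or with a complication of hepatitis B virus carrier". No MedDRA terms and no HBV-DNA criterion are given.

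The results tables in SAP 8.2.3.1 carry the same limit: "Hepatitis B virus reactivation (in patients with past history or complication of hepatitis B virus carrier". SAP 8.2.3.2 repeats it for adverse events.

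Among the patient characteristics in SAP 8.2.2, "Hepatic function disorder: past history of hepatitis B [absent, present" and "Hepatic function disorder: past history of hepatitis B virus carrier [absent, present" are separate lines, and the complications list has the same split. Protocol 7.3.7.5 collects, before treatment, "Hepatitis B virus test: HBs antigen, HBs antibody, HBc antibody, and HBV-DNA test".

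**The concern.** Every other element in SAP 6.1 is defined by the event, through coded terms and, for infections, seriousness. This one also depends on what was written in the patient's history. A case in a patient without a carrier entry can therefore be reported, coded and stored, and still not reach the row that is meant to report the risk.

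The study was imposed as an approval condition to collect safety data in all treated patients. If the row read zero while a term naming reactivation stood in the SOC/PT table, a reader of the safety-specification results would be misled about an identified risk. The same rule feeds the onset table and the dose analyses and Kaplan-Meier plots of SAP 8.2.3.3.

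**Working it through.** The point rests on wording, so the check applies the rule to example records. No sample size, power or event count enters it, and the plan states no figure for this element that could be reproduced.

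**Inputs**
- Risk as named: no limit to carriers (Protocol 6.1.1; SAP 2.1).
- Counting rule: a hepatitis B event, plus a past history or complication of carrier (SAP 6.1, 8.2.3.1, 8.2.3.2).
- Alternative definition: none, as the SAP says the periodic report has none.
- Source of past history and complications: the CRF medical-history entry (SAP 8.2.2).
- Serology: collected before treatment (Protocol 7.3.7.5), summarised descriptively in SAP 8.2.2, and absent from the rule.
- Adverse events: all are collected to Week 60, in carriers and non-carriers alike (SAP 2.1).

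**Applying the rule.** In each record the reported adverse event is hepatitis B reactivation, within 60 weeks.

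| Record | Medical-history entry | Pre-treatment serology | Carrier condition met? | Counted? |
|---|---|---|---|---|
| 1 | HBV carrier | any | yes | yes |
| 2 | past hepatitis B only | HBc antibody positive, HBs antigen negative | no, on a literal reading | no |
| 3 | none | HBc antibody positive | no | no |
| 4 | none | HBs antigen positive | no | no |

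Record 2 turns on SAP 8.2.2 keeping hepatitis B and carrier as different items. Record 3 turns on serology having no role in the rule. Record 4 is partly a data-quality matter, because an antigen-positive patient with no history entry is a discrepancy that the query process in Protocol 7.6.5.2 could resolve. Records 2 and 3 carry the point.

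**Where an uncounted case goes.** It leaves this element's count, proportion, incidence with its confidence interval, and onset table. If judged related to treatment, it also leaves the dose analyses and the Kaplan-Meier plot. It stays in the SOC/PT tables and the listings. It also enters serious infections if it is serious and coded to that SOC, and hepatic function disorder if it is coded to one of that element's terms.

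**Size.** Neither document gives the number of carriers, of patients with past hepatitis B or of antibody-positive patients, or a reactivation rate in any of them. The number of missed events cannot be calculated. For scale only, one uncounted case in the planned safety set of 470 is 1/470 = 0.2% of patients.

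**Related gaps**
- The SAP does not say whether this element's denominator is the carriers or the whole safety set.
- SAP 8.2.2 summarises a pre-treatment HBc antigen test, whereas the protocol collects HBc antibody.
- Protocol 7.3.7.5 asks for on-treatment HBV-DNA status only in carriers.

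**The case against.** The limit looks deliberate and has a rationale. Carriers are the only group for whom on-treatment HBV-DNA status is requested, and SAP 5.4.2 makes carrier status a safety subgroup. An element confined to the group with planned HBV-DNA recording is internally consistent, and the unrestricted wording elsewhere is a risk heading, not a case definition. This stands as a reason to keep a carrier row. It does not justify having no row for reported cases in anyone else.

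Carrier is also undefined. Protocol 7.3.2 describes history as conditions cured before treatment, so a past-carrier entry might be used for resolved infection, and one patient can be positive on both lines of SAP 8.2.2. Coding rules outside the documents could narrow the gap. This stands too: record 2 is excluded on a literal reading, not with certainty. The separate lines still point towards exclusion, and the ambiguity itself needs settling.

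Two stronger readings are tempting:
- A reader might infer that such cases vanish from the study. They do not: all adverse events are collected to Week 60, and these cases remain in the SOC/PT tables and listings. Those outputs, however, give no reactivation incidence.
- A reader might assume prevalences of carriage and past infection and conclude that most reactivations are missed. The documents give no such prevalences, and the result would be a share of patients, not of missed events.

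**Conclusion.** The concern holds as a mismatch between an unrestricted identified risk and a restricted counting rule. Followed as written, the SAP leaves a reported reactivation in a patient without a carrier entry out of the element that reports this risk. The effect is confined to that element and what is derived from it; the data are not lost. Its size is unknown and could be nil if no such case is reported.

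The conclusion assumes that carrier means what the separate lines of SAP 8.2.2 suggest, a category distinct from past or concurrent hepatitis B and not derived from serology.

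**What to change.** In SAP 6.1, 8.2.3.1 and 8.2.3.2:

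1. List the MedDRA terms for hepatitis B reactivation, hepatitis B and HBV-DNA increase. Count any adverse event coded to them in all patients of the safety analysis set, with that set as the denominator for both the proportion and the person-years.
2. Present the same events by baseline status: carrier; past or concurrent hepatitis B without a carrier entry; serology-positive only; none or not tested. Give each row its own matching denominator, so that no patient is in a numerator without being in the denominator.
3. Keep the current carrier-only row.
4. Define carrier, and state which serology results make a patient serology-positive. Reconcile HBc antigen in SAP 8.2.2 with HBc antibody in Protocol 7.3.7.5 before HBc status is used.

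The cost is SAP wording, a term list and a baseline-status derivation from history and serology that the protocol already collects, once the HBc mismatch is settled. The downside to state in the report is weaker ascertainment outside the carrier group, where on-treatment HBV-DNA status is not requested. Incidence there, and in the safety set as a whole, may be understated. The carrier row is kept for that reason.

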- Prior vaccination with a tuberculosis vaccine [absent, present]
- Prior vaccination with a pneumocystis jirovecii pneumonia vaccine [absent, present]
- Prior vaccination with a hepatitis B vaccine [absent, present]
- Prior treatment with a non-drug therapy [absent, present]
- Prior treatment with a non-drug therapy: blood cell component removal therapy [absent, present]
- Prior treatment with a non-drug therapy: surgery [absent, present]
- Baseline neutrophil count [<2000/μL, ≥2000/μL, not tested]
- Baseline lymphocyte count [<1000/μL, ≥1000/μL, not tested]
- Baseline hemoglobin [$\leq 8 \text{ g/dL}$, $\geq 8 \text{ g/dL}$, not tested]

Using the SAS, patients will be summarized according to the following factors in terms of n and proportion by SOC and PT:

- Past history (diseases and syndromes recorded as past history in the CRF entry "Medical history")
- Complications (diseases and syndromes recorded as present illness in the CRF entry "Medical history")

Using the SAS, patients will be summarized according to the following factors in terms of n and proportion:

- Pre-treatment testing for hepatitis virus [absent, present]
- Pre-treatment HBs antigen test [positive, negative, not tested]
- Pre-treatment HBs antibody test [positive, negative, not tested]
- Pre-treatment HBc antigen test [positive, negative, not tested]
- Pre-treatment HCV antibody test [positive, negative, not tested]
- Pre-treatment imaging [absent, present]
- Pre-treatment imaging: chest X-ray [normal, abnormal, not tested]
- Pre-treatment imaging: chest CT [normal, abnormal, not tested]
- Pre-treatment interferon gamma release assay [absent, present]
- Pre-treatment interferon gamma release assay: QuantiFERON [positive, equivocal, negative, indeterminate, not tested]
- Pre-treatment interferon gamma release assay: T-Spot. TB [positive, equivocal, negative, indeterminate, not tested]
- Pre-treatment tuberculin reaction [-, 1+, 2+, 3+, indeterminate, not tested]
- Pre-treatment diastolic blood pressure [<60 mmHg, ≥60 to <80 mmHg, ≥80 to <100 mmHg,
 ≥100 to <120 mmHg, ≥120 mmHg, not measured]

Pre-treatment systolic blood pressure [<120 mmHg, ≥120 to <140 mmHg, ≥140 to <160 mmHg,
 ≥160 to <180 mmHg, ≥180 mmHg, not measured]

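### The SAP counts hepatitis B reactivation only in patients recorded as carriers, so events in patients identified by baseline tests or by a recorded past hepatitis B are left out of that element

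*SAP*

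**What the plan says.** Protocol 6.1.1 lists "Reactivation of hepatitis B virus" among the important identified risks, and SAP 2.1 carries the item over. Neither place restricts it to carriers.

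SAP 6.1 takes the definitions of the safety-specification elements from the periodic safety update report, "except for hepatitis B virus reactivation, of which definition is given in this SAP below, because it is not defined in the PSUR". The definition it then supplies has two parts: "Events associated with hepatitis B that developed in patients with", followed by the patient restriction "past history of hepatitis B virus carrier or with a complication of hepatitis B virus carrier". SAP 8.2.3.1 (adverse reactions) and 8.2.3.2 (adverse events) attach the same restriction in parentheses.

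Under SAP 8.2.2, past history and complications come from the medical history entry of the CRF. That section lists hepatitis B and hepatitis B carrier status as separate items, both for past history and for complications.

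Protocol 7.3.7.5 asks for the results of hepatitis B tests done in the 3 months before treatment: "HBs antigen, HBs antibody, HBc antibody, and HBV-DNA test". After treatment starts, the recording narrows: "For patients who are HBV carriers, the status of HBV-DNA test conducted up to the completion of the observation period". SAP 8.2.2 tabulates pre-treatment hepatitis tests. One row reads "Pre-treatment HBc antigen test [positive, negative, not tested", which is not a test the protocol lists. There is no row for HBc antibody and none for baseline HBV-DNA.

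**The concern.** The stated risk is reactivation in treated patients. The analysis narrows it to reactivation in patients whom an investigator has labelled as carriers. The study records baseline serology and viral DNA, which could identify further patients with evidence of current or past infection, and the endpoint makes no use of them. Because the definition is the SAP's own, no external definition compels this.

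At stake is whether this identified risk can be read at face value from its own row. If a hepatitis B event occurs in a patient without a carrier entry, the row for reactivation does not show it. Someone reading the safety-specification tables could then see a zero, or too low a count, and have to find the event elsewhere under another name.

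**Working it through.** The documents state no expected rate, event count or sample size for this element. The planned 470 patients rest on herpes zoster. The check is therefore a comparison of the text, with one small illustration.

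**Step 1: who enters the element.** The filter is a carrier entry in the CRF medical history (SAP 6.1 with 8.2.2). Protocol 7.3.2 treats history as disease that is cured, and concurrent disease as disease that needs treatment or leaves residual symptoms. A symptom-free patient known only from a positive test fits neither field well. Neither document says whether a positive HBs antigen or HBV-DNA result by itself makes a patient a carrier.

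| Patient with a hepatitis B-associated event | Counted in the element as written? |
|---|---|
| Carrier entry in medical history | Yes |
| Hepatitis B recorded, no carrier entry | No: SAP 8.2.2 treats these as different items |
| Positive baseline HBs antigen, HBc antibody or HBV-DNA, nothing in medical history | No: no rule uses the result |
| Positive HBs antibody only | No, and the result may reflect vaccination |

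**Step 2: which outputs are affected.** The element feeds the number and proportion of patients, the incidence with its 95% CI and the onset-timing tables (SAP 8.2.3.1 and 8.2.3.2), and the dose-subgroup summaries and Kaplan-Meier plots (SAP 8.2.3.3). An event in the second or third row of the table is absent from all of them.

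**Step 3: where the event can still be seen.**
- The overall SOC/PT tables (SAP 8.2.3.1 and 8.2.3.2) and the listings (SAP 9) do not depend on carrier status.
- If it is serious and coded to the infections SOC, it counts under serious infections (SAP 6.1).
- If it is reported as raised transaminases or hepatic enzymes, or is retrieved by the hepatic SMQ, it counts under hepatic function disorder (SAP 6.1).

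None of these routes labels it as reactivation.

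**Step 4: what one uncounted event does.** SAP 8.1.4 gives the upper 95% limit per 100 patient-years as (100/PT) × ½ × χ² at 0.975 with 2(y+1) degrees of freedom. Hold PT fixed as a simplification.
- y = 1: the half chi-square value is 5.57, so the limit is 557/PT.
- y = 0: the half chi-square value is 3.69, so the limit is 369/PT.

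The ratio is 3.69/5.57 = 0.66. Dropping a single event takes the count from 1 to 0 and lowers the upper limit by about a third. This shows sensitivity only and does not imply that such an event occurs.

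**The case against.** The best defence is that the SAP matches the data. The protocol records on-treatment HBV-DNA only for carriers, so carriers are the one group with recorded virological follow-up. Pooling them with patients whose events surface only as spontaneously reported AEs could dilute the incidence and suggest a comparability that is not there. This stands as a reason to keep the carrier row intact and not to merge groups. It does not justify having no row for the others, since all AEs are collected for every patient up to 60 weeks (SAP 2.1).

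Three stronger readings are tempting, and the documents do not support them.
- A reader might infer that an event in a non-carrier disappears from the report, or survives only as one line of a SOC/PT table. Step 3 shows other routes. In addition, SAP 5.4.2 makes the 8.2.2 characteristics safety subgroups, and these include recorded hepatitis B.
- A reader might infer that non-carriers are also outside the denominator. The SAP does not say whether this element is divided by carriers or by the whole safety analysis set. The parenthesis in 8.2.3.1 and 8.2.3.2 may only restate the event definition, and 8.1.4 sets no carrier denominator. Only the effect on the numerator is certain.
- A reader might want to put a number on the excluded patients. The documents give no frequency of positive serology without a carrier entry, so any range would be guesswork.

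It is also fair to say that an investigator who sees a positive test may enter carrier status, in which case the patient is counted. The HBc antigen label may be a translation slip, since the SAP carries a translation record from a Japanese original. That cannot be confirmed here, and it concerns a descriptive table, not the endpoint.

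**Conclusion.** The point holds as a gap in the definition of one identified-risk element. As written, hepatitis B-associated events in patients known only from baseline tests, or with hepatitis B recorded but no carrier entry, are left out of the reactivation count, incidence, onset and Kaplan-Meier outputs. The safety information itself is not lost; what is lost is its attribution to this risk.

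The number of patients affected cannot be derived. The conclusion rests on reading the carrier restriction literally and on the absence of any SAP rule that turns a test result into carrier status. If the sponsor applies such a rule in practice, the gap shrinks to patients outside that rule, and the rule should be written down. The unstated denominator and the mismatch between the tests recorded and the tests tabulated are smaller defects that should be corrected together with it.

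**What to change.** In SAP 6.1, 8.2.3.1 and 8.2.3.2:
- Keep the present carrier row, and say how carrier status relates to baseline test results.
- Add a separate row for hepatitis B-associated events in non-carriers who have recorded hepatitis B or a positive baseline HBs antigen, HBc antibody or HBV-DNA result.
- Show patients positive for HBs antibody alone in their own row, or leave them out. They may be vaccinated, and a carrier/non-carrier split cannot tell them from patients with past infection.
- State the denominator of each row, and say where untested patients are placed.
- Do not combine the rows into one incidence without comment. Add a note that on-treatment HBV-DNA is recorded only for carriers, so detection in the other rows rests on reported AEs.

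In SAP 8.2.2, tabulate HBc antibody in place of HBc antigen and add baseline HBV-DNA.

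The cost is SAP wording, one or two table rows and a footnote, using data the protocol already records. The small downside is weaker ascertainment in the new row, which the footnote discloses. Nothing in patient care or testing changes.
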